7.5. Withdrawal Criteria

Participants have the right to withdraw from the trial at any time without having to give a reason. Investigator sites should try to ascertain the reason for withdrawal and document this reason along with the withdrawal itself within both the CRF/CDMS, on a trial withdrawal form and participant's clinical notes in order ensure that information relevant to the trial design, medication tolerability and efficacy is collected where possible.

Please note there is **no requirement** to withdraw from the trial due to participants electing to discontinue trial treatment or investigator-led treatment discontinuation, please see section 7.6. Participants who discontinue trial treatment can continue to complete all remaining assessments at distance, however, if this is not possible all efforts should be made to ensure that the research assessments at 36 weeks are completed as a minimum.

If participants who discontinue trial treatment plan to begin a new therapy for TMD (NHS or private) within the remainder of the trial monitoring period, they should be asked if they will complete the next set of research assessments prior to beginning a new treatment in routine clinical care and then go back on schedule to the next scheduled set of research assessments following this.

The PI, CI, or other delegated individual may withdraw a participant from the trial at any time if they consider it necessary for any reason including (but not limited to) the following reasons:

- Loss of capacity
- Pregnancy
- Symptomatic deterioration
- Unacceptable toxicity
- Sustained and significant issues with tolerance of any of the IMPs used
- Significant protocol deviation or non-compliance
- Investigator's discretion that it is in the best interest of the participant to withdraw them. As examples this might include, but is not limited to, the following situations: continued participation in the trial would place unreasonable demands on the participant's physical or psychological health; participant loses capacity for a prolonged period; participant experiences an adverse event, which in the opinion of the investigator results in the inability to continue to comply with the trial. The participant would be informed of the decision and return to their routine care pathway in the NHS.
- Notification of an adverse event using the IMP in another trial; or with any of the interventions in routine clinical practice, which in the interpretation of the investigators, may potentially put trial participants at risk.
- Termination of the clinical trial by the sponsor

The PI or their delegate will record the withdrawal status and reason on the CRF.

If a trial participant withdraws/is withdrawn from the trial, all data collected to the point of withdrawal will be retained and included in analysis. This point is included in the consent for the trial.

Those who withdraw/are withdrawn from the trial will return to having their M-TMD managed by their referring/treating clinician as per routine care in the NHS. For those on medications in the TAU arm a suitable taper off schedule will be suggested to the patient's GP within the letter explaining they have withdrawn.

7.6. Discontinuation of trial treatment

Participants may elect (or investigators may elect for participants) to stop receiving any of the IMPs and remain on the trial. Participants will continue to take part in trial assessments as per the schedule of events except for the MRI sub-study if they are enrolled in this. After discontinuation, if they elect to begin a new therapy for TMD within routine clinical care (NHS or private), they will be asked to complete the next set of research assessments that are due prior to beginning the new treatment and then go back to the regular schedule following this and the new treatment details recorded in their clinical notes and CRF.

Discontinuation of treatment along with a reason, if possible, will be recorded in the clinical notes and the CRF. A discontinuation from treatment form will also be completed and stored in the ISF.

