3.2. Secondary Objective(s)

- a) To assess cost-effectiveness in terms of incremental cost per QALY over a lifetime horizon.
- b) To evaluate whether the interventions affect generic quality of life (EQ-5D-5L).
- c) To examine responder rates and adherence over time in all interventions.
- d) To evaluate whether any of the interventions affect jaw function.
- e) To evaluate whether any of the interventions affect psychosocial distress, sleep quality, or analgesia use.
- f) To compare the adverse effect profiles of the interventions including the MRI sub study examining changes in the temporomandibular joint.
- g) To explore treatment experiences and acceptability of interventions.

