7.1.5. Randomisation

Those who provide informed consent and fulfil eligibility criteria will be randomly allocated stratified by psychosocial status (PHQ-4 score≥6 (Penlington et al., 2020)) and site in a ratio of 1:1:1 to one of the three arms of the study: TAU, lidocaine injections, or Botulinum toxin type A injections 3 monthly for 3 cycles (weeks 0, 12, 24). The randomisation process will use the Sealed Envelope (SE) system (a central, secure, 24-hour web-based randomisation system with concealed allocation). The SE system will use random permuted blocks within strata. Those who have been delegated the randomisation task at local sites will be provided with personal login IDs and passwords. The study is open label. Those participating in the trial north-east of England (Newcastle, Sunderland, Middlesbrough sites) will be offered the opportunity to participate in the optional MRI sub-study. Seventeen participants from each arm of the trial will be sequentially selected from those who opt-in to the sub-study making a total of 51 participants in the sub-study.

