7.4.8. MRI sub-study assessments

Each of the 51 participants recruited into the MRI sub-study (17 from each arm of the study in the North East of England) will undergo two MRI scans of their temporomandibular joints, and temporalis and masseter muscles. The first scan will take place between trial visit 1 and visit 2 (day -28 to -1) and must be prior to commencement of trial intervention, where possible. The second MRI visit will occur within +/- 7 days of the week 36 visit. MRI scans will take place at the Centre for In Vivo Imaging, Newcastle University. Each MRI scan will take approximately 1 hour. If for any reason an MRI scan is of insufficient quality for research assessments, if appropriate, a repeat scan may be arranged with the participant's consent.

Any incidental findings during the MRI procedure will be identified by the radiologist reviewing the scan, who will report to the Newcastle clinical team, who will contact the patient to discuss the finding and inform the local site team and GP/Dentist/Consultant as appropriate. Further monitoring, investigation, or treatment, as appropriate, would then be conducted in the usual NHS care pathways for the finding identified. If the finding clearly and unambiguously nullifies the M-TMD diagnosis or meets another exclusion criteria, the patient would be withdrawn from the trial and informed of this whilst discussing the finding with the clinical team. Otherwise, as long as the patient was happy to continue in the trial, this would be possible.

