A venous blood sample totalling approximately 4 – 6 mL in an EDTA tube will be taken at each of the two MRI visits. Each sample will be used to measure serum biomarkers of bone turnover CTX and P1NP at screening and at 36 weeks. Samples will be labelled in accordance with the Sponsor's usual requirements and will be transported, stored, accessed, and processed in accordance with national legislation relating to the use and storage of human tissue for research purposes and such activities shall at least meet the requirements as set out in the 2004 Human Tissue Act. Once blood samples have been analysed, they will be disposed of in accordance with local site protocols. Analysis will take place in the Sponsor's clinical laboratories (Newcastle Laboratories) or via Newcastle Laboratories as part of a service level agreement with an external laboratory in compliance with the UK Data Protection Act 2018, the UK GDPR as amended on 01 January 2021 by regulations under the European Union (Withdrawal) Act 2018, and the 2004 Human Tissue Act. If it is not possible to perform analysis on the blood sample for any reason (e.g., degraded sample, insufficient sample), if appropriate, a repeat sample will be obtained with the participant's consent.

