10.2.2. Analysis of Secondary Outcome Measures

Secondary outcomes will be analysed for superiority of each intervention against TAU. All analyses will be in the ITT population i.e. following a treatment policy approach. Estimated differences between treatment groups will be reported with two-sided 95% confidence intervals.

Secondary patient-reported outcomes (PHQ-4, BPSQI, SF-JFLS, GIC, Liverpool adverse effects profile, FaCE) will be analysed using linear mixed effects regression models similar to the co-primary outcomes above, but with the baseline value of the corresponding outcome included as a fixed effect. Domains or individual items may also be reported and analysed using appropriate regression techniques as described in the SAP. Analgesia use at any time during the trial will be analysed as a binary outcome using mixed effects logistic regression with a random effect for site and fixed effects for treatment and the stratification factor of psychosocial status. The secondary outcomes of 30% and 50% reduction from baseline in CPI and OHIP-TMD will be analysed separately at each timepoint using mixed effects logistic regression with a random effect for site and fixed effects for treatment, baseline score and the stratification factor of psychosocial status.

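### Participants who stop trial treatment leave the MRI sub-study, so week-36 joint imaging and bone markers describe continuers only, contrary to the stated treatment-policy approach

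*Protocol*

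**What the plan says.** Section 7.6 allows treatment to stop without leaving the trial: "Participants may elect (or investigators may elect for participants) to stop receiving any of the IMPs and remain on the trial". Either side may decide and no particular reason is required. Those who stop continue with assessments "as per the schedule of events except for the MRI sub-study if they are enrolled in this". No reason is given for the exception.

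The sub-study is small and has one follow-up point. Section 7.1.5: "Seventeen participants from each arm of the trial will be sequentially selected from those who opt-in to the sub-study making a total of 51 participants". Section 7.4.8 states that each of the 51 has two scans, and fixes the later one: "The second MRI visit will occur within +/- 7 days of the week 36 visit". The bone markers are tied to the same visits: "A venous blood sample totalling approximately 4 – 6 mL in an EDTA tube will be taken at each of the two MRI visits".

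The sub-study serves secondary objective f (section 3.2), the comparison of adverse-effect profiles, "including the MRI sub study examining changes in the temporomandibular joint". TMJ structure, apparent diffusion coefficient (ADC), CTX and P1NP are listed as secondary outcomes in section 3.3.2. For secondary outcomes, section 10.2.2 says: "All analyses will be in the ITT population i.e. following a treatment policy approach".

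**The concern.** A treatment-policy estimate needs the outcome measured whether or not treatment was continued. For the MRI and biomarker outcomes, the protocol instructs sites not to measure it once treatment stops. An analysis plan can choose how to handle missing values, but it cannot recover scans and bloods that were never taken.

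What is at stake is the population to which the joint-safety result applies. Stopping happens after randomisation and may be related to adverse effects, lack of benefit or other reasons. If those who stop differ in joint or bone outcome from those who continue, the continuers' result does not carry over to everyone treated. If stopping differs between arms, the arm comparison is affected too.

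**Working it through.** **Side by side**

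| Place in protocol | What it implies for a sub-study participant who stops treatment and stays in the trial |
|---|---|
| 7.4.8 | Second scan at week 36, as one of the 51 |
| 7.4.8 (blood sample) | CTX/P1NP taken at that visit and not otherwise after baseline |
| 7.6 | Leaves the MRI sub-study |
| 10.1 | In the ITT population if there is any post-baseline assessment, such as a week-12 questionnaire |
| 10.2.2 | Analysed under a treatment-policy approach |

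Such a participant belongs to the analysis population but has no MRI, ADC, CTX or P1NP value after baseline. No other section restores the scan or the sample.

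**Why stopping may differ by arm.** Sections 7.4.10 and 8.4 place injections at day 0, week 12 and week 24. Someone who has had all three cycles has no later dose to stop, so the exception can no longer apply. Oral medication in the TAU arm can be stopped at any time up to week 36; a schedule footnote provides for participants still taking it then or stopping after week 35. The window in which the rule can remove a scan is therefore longer in TAU.

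**Size.** The protocol's own total reproduces: 3 × 17 = 51. It gives no discontinuation rate, so I assume 10% to 25%.

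- Per arm: 17 × 0.10 = 1.7 and 17 × 0.25 = 4.25, so about 2 to 4.
- Overall: 51 × 0.10 = 5.1 and 51 × 0.25 = 12.75, so about 5 to 13.

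These are scans lost by rule. The number recoverable is smaller, because some discontinuers would decline and some would withdraw fully.

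**Precision.** The protocol states no power for the sub-study. As an illustration, the standardised difference detectable with 80% power at two-sided 5% is about (1.960 + 0.842) × √(2/n):

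- n = 17: 2.802 × 0.343 = 0.96 SD
- n = 15.3 (10% stop): 2.802 × 0.362 = 1.01 SD
- n = 12.75 (25% stop): 2.802 × 0.396 = 1.11 SD

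The loss of precision is modest. The sub-study can detect only large differences either way.

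**Selection.** Suppose, purely as illustration, that a joint change occurs in 10% of continuers and k times as often in discontinuers. With a fraction d stopping, the risk in all treated is 10% × [(1 − d) + d × k].

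| d | k = 0.5 | k = 2 | k = 5 |
|---|---|---|---|
| 10% | 9.5% | 11% | 14% |
| 25% | 8.75% | 12.5% | 20% |

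The sub-study would show about 10% in every cell. The gap can go either way, and a larger sample would not close it.

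**The case against.** The best defence is that the rule touches little. Adverse event reporting, the Liverpool profile, facial-weakness and clinical examinations continue for discontinuers, so most of objective f is intact. The sub-study has 17 per arm and no stated power. Discontinuers have had less exposure, and including them may dilute a drug effect. A result in participants who completed treatment is meaningful in its own right. All of this is fair, and it limits the reach of the point. It does not remove the conflict between 7.6 and sections 7.4.8 and 10.2.2.

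A reader might infer more than the documents support:

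- **That only those who tolerated treatment are scanned.** Section 7.6 covers stopping for any reason, and a participant who tolerated all three injections badly is still scanned. The retained group is continuers.
- **That about 27% would lose their scan.** In section 10.3 this is worst-case loss to follow-up, not treatment discontinuation. People lost to follow-up would miss the scan under any rule.
- **That a treatment-policy analysis becomes impossible, or a null result uninterpretable.** Such an estimate would rest on untestable assumptions about the unmeasured values. A null result can still be read for continuers.
- **That the exception breaks an otherwise intact randomised comparison.** Participants are selected sequentially from those who opt in at the North-East sites, randomisation precedes the first scan, and the trial is open label. Some selection after allocation may already exist; the exception adds to it.
- **That harm is being hidden.** Nothing in the documents establishes the direction of bias.

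The request in section 7.5 for week-36 assessments from discontinuers lends little support, since it is framed around completion at a distance, which an MRI cannot be.

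**Conclusion.** The point holds for the imaging and biomarker part of the adverse-effect objective. Section 7.6 confines week-36 MRI, ADC, CTX and P1NP to participants who continued treatment, which cannot be squared with two scans for each of the 51 or with a treatment-policy analysis. A conclusion of no joint change would apply to continuers only. The 2 to 4 of 17 per arm losing the scan by rule rests wholly on the assumed 10-25% discontinuation. The possible imbalance between arms follows from the treatment schedules, but its size is unknown. The co-primary outcomes, questionnaires and other safety data are not affected. The change is worth making because it is cheap and the missing data cannot be recovered later.

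**What to change.** Delete the MRI exception in section 7.6. Invite discontinuers who remain in the trial, consent and can still safely be scanned to the week-36 MRI and blood sample, and record the injection cycles or oral drug exposure they received. Analyse all scanned participants as randomised, report by arm how many were and were not scanned and why, and add a description by exposure received.

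The cost is one clause in the protocol, plus matching participant information if it repeats the exception. Scans and assays are already planned for all 51. The downside is that some will decline, leaving part of the selection in place, and that reduced exposure may dilute an effect; the description by exposure helps the reader judge this.

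If there is a reason to keep the exception, state it, correct section 7.4.8, and say in section 10.2.2 that the MRI and biomarker results describe continuers only and are not a treatment-policy estimate.

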^b All research assessments will be collected up to 7 days ahead of any IMP administration at these visits and prior to administration of any further IMP. New local prescriptions will be issued by the GP following instruction from the site teams at weeks 12 and week 24, or by sites for their pharmacy at 12 weeks and at 24 weeks for the patient to collect in the TAU arm.

^c All research assessments will be collected up to 7 days ahead of any IMP administration at these visits and the CRF updated at the visit.

^d Confirmed in writing in the clinical notes at each study visit.

^e Pregnancy test required at 36 weeks for all participants of childbearing potential or 7 days after this point if participants are still on TAU week 36^e

fMigraine history and MIDAS only repeated if positive at any of the previous visits. If reporting a new headache then ID-Migraine, migraine history and MIDAS are completed at that visit and the migraine history and MIDAS are repeated at subsequent visits.

§ Phone call to collect AE data in 7 days since week 36 visit. Only required if participant still receiving TAU IMP at week 36 or stopped IMP after week 35.

^h Qualitative interview will ideally take place during screening but may be up to 4 weeks after consent to the interview. This may be after the start of the IMP in some cases.

TAU prescription may be issued at any point during screening or at Day 0 as appropriate. Day 0 is the first dose of IMP.

Review of medication only at week 36

IMPORTANT: If participants who discontinue trial treatment plan to begin a new therapy for TMD (NHS or private) within the remainder of the trial monitoring period, they should be asked if they will complete the next set of research assessments prior to beginning a new treatment in routine clinical care and then go back on schedule to the next scheduled set of research assessments following this.

Key
AE & SAE - Adverse Event & Serious Adverse Event
BPSQI - Brief Pittsburgh Sleep Quality Index
CN V & VII - 5th Cranial Nerve and 7th Cranial Nerve
CPI (within GCPS) - Characteristic Pain Intensity (Graded Chronic
Pain Scale)
EQ-5D-5L - See section 7.4.6.4
FaCE - Facial Clinimetric Evaluation
GIC - Global impression of change

HUQ – Health Utilisation Questionnaire
MIDAS – Migraine Disability Assessment Test
LAEP - Liverpool adverse events profile
OHIP-TMDs - Oral Health Impact profile for TMD
PHQ-4 - Patient Health Questionnaire-4
PMH – Past Medical History

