10.2.1. Analysis of the Co-primary Outcome Measures

The main co-primary objective is to estimate the mean difference in disorder specific quality of life measured by OHIP-TMD and pain intensity measured by CPI at 36 weeks in adults with chronic (≥3months) myalgia temporomandibular disorder (M-TMD) treated with BTX compared to TAU and Lidocaine injections compared to TAU, regardless of deviations from the allocated treatment for any reason. The estimand is described by the following attributes:

Estimand attribute	Description
Population	Adults with chronic (≥3months) myalgia
	temporomandibular disorder (M-TMD)
Treatment conditions	1. BTX injections (intervention)
	2. Lidocaine injections (intervention)
	3. TAU, amitriptyline/gabapentin (control)
Outcome measures	1. Disorder specific quality of life measured by
	OHIP-TMD at 36 weeks
	2. Pain intensity measured by CPI at 36 weeks
Strategies used to handle intercurrent events	1. Deviation from treatment for any reason –
	treatment policy ¹
	2. Initiation of alternative treatments –
	treatment policy ¹
	3. Death – hypothetical ²
Population-level summary measures	1. Mean difference in OHIP-TMD at 36 weeks
	(adjusted for baseline) between each
	intervention and control
	2. Mean difference in CPI at 36 weeks
	(adjusted for baseline) between each
	intervention and control

¹The treatment policy strategy targets the treatment effect regardless of the occurrence of intercurrent event.

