10.3. Sample Size Calculations

The sample size will be 663 which has been chosen to provide high power for both the OHIP-TMD and CPI co-primary outcomes (Durham et al., 2021; Dworkin et al., 2008; Yule et al., 2015; Collignon et al., 2020).

From Yule et al, the standard deviation (SD) of OHIP-TMD is 20.7 at 12 weeks (Yule et al., 2015), which we expect to be consistent at subsequent measurement times. The correlation with baseline was 0.6. To have 90% power (two-sided 5% type I error rate) to detect a difference between arms equal to the minimally important clinical difference (MICD) of 6.0 would require 251 per arm; taking the correlation into account would reduce this to $(1-0.6^2)*251 = 161$ per arm. We have inflated this by 27% to account for worst-case scenario loss-to-follow up identified between two large research studies we have conducted involving treatment and M-TMD (Durham et al., 2021; Yule et al., 2015). This gives a required sample size of 663.

This sample size provides extremely high power (>99%) to detect differences between arms in the CPI, which we assume has an SD of 20 based on the DEEP study (Durham et al., 2021) and MICD of 10 (Dworkin et al., 2008). To conclude superiority, statistically significant differences in both OHIP-TMD and CPI will be needed, meaning that an adjustment for multiple testing is not required and that the overall power is approximately 90% for each separate comparison (BTX vs TAU and Lidocaine vs TAU). As per consensus on multi-arm trials with distinct interventions, we do not formally adjust for multiple intervention arms (Collignon et al., 2020), but the total chance of recommending an ineffective intervention as superior to TAU is <5%. The quantity and timing of attrition will be monitored. If the attrition rate by 36 weeks increases above the estimated 27%, we may increase the sample size to maintain the power of the trial in agreement with the trial's oversight committees and subject to funding and time constraints.

11. Economic Analysis

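### Participants who stop trial treatment and start a new TMD therapy after week 24 are asked for their week-36 CPI and OHIP-TMD before the switch, which conflicts with the treatment-policy estimand

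*Protocol*

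**What the plan says.** **Estimand.** Protocol 10.2.1 targets the mean difference in OHIP-TMD and CPI at 36 weeks "regardless of deviations from the allocated treatment for any reason". Its attribute table assigns treatment policy to two intercurrent events: deviation from treatment, and initiation of alternative treatments.

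**Timing.** Section 7.4.4 puts visit 5 at week 36 ±7 days. Section 3.3.1 defines the week-36 CPI over the preceding 12 weeks and the week-36 OHIP-TMD over the preceding 4 weeks.

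**Switching rule.** For participants who have discontinued trial treatment and plan a new TMD therapy, 7.6 says "they will be asked to complete the next set of research assessments that are due prior to beginning the new treatment". The note under the schedule of events (7.4.10) says "they should be asked if they will complete the next set of research assessments prior to beginning a new treatment in routine clinical care", and 7.5 carries the same request. All three then send the participant back to the regular schedule. Section 7.5 and the note specify the scheduled set that comes after the one just completed.

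**Safeguards.** Section 7.5 says that stopping treatment does not require leaving the trial, and asks sites to try hard to obtain at least the week-36 set from discontinuers. Section 7.6 keeps discontinuers on the normal assessment schedule, apart from the MRI sub-study.

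**Withdrawal.** Section 7.5 allows the investigator to withdraw a participant from the trial. Listed grounds include deterioration, toxicity, tolerance problems and "Significant protocol deviation or non-compliance". After that, "all data collected to the point of withdrawal will be retained and included in analysis".

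**The concern.** A treatment-policy estimand for starting an alternative treatment needs the outcome after that start, at the defined time. For one group the conduct rule asks for the last remaining set before the start and schedules nothing afterwards. The post-switch week-36 value is then never observed. If the early set is labelled week 36, it enters the model as an on-time value. If it is excluded as out of window, week 36 is missing and is modelled under missing at random. Neither gives what 10.2.1 defines.

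The trial is open label, both co-primaries are self-reported, and oral and injected treatments end differently. The size of the affected group may therefore differ by arm, and a difference of that kind shifts the primary contrast.

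**Working it through.** **1. Which participants are affected.**

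| Event | Next due set | Effect on week 36 |
|---|---|---|
| Stops treatment, no new therapy | unchanged | none |
| New therapy before the week-12 set is due | week 12, taken early | none |
| New therapy after week 12, before the week-24 set is due | week 24, taken early | none |
| New therapy after the week-24 set, before week 36 | week 36, taken early | pre-switch value, no later set |

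Only the last row conflicts with the estimand.

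**2. How far off the timing can be.** Take a set completed at week 25. The window opens at week 35, so the set is 10 weeks outside it. Its CPI covers weeks 13–25 instead of 24–36, and its OHIP-TMD covers weeks 21–25 instead of 32–36.

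**3. Which arms are affected.** Injections are given at day 0, week 12 and week 24 only (8.4 and 7.4.10). After the third cycle an injection participant has nothing left to discontinue, so on its wording the rule does not apply. A switch at week 28 would leave that participant's week-36 set on time and post-switch. TAU can still be running at week 36 (schedule footnotes on the pregnancy test and the safety call), so a TAU participant can discontinue after week 24 and fall under the rule. So can an injection participant who missed or declined a cycle. This is an inference from the wording; the protocol does not say it.

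**4. The plan's own figures (10.3).** Inputs: "the standard deviation (SD) of OHIP-TMD is 20.7 at 12 weeks"; the "minimally important clinical difference (MICD) of 6.0 would require 251 per arm"; 90% power, two-sided 5%; baseline correlation 0.6; loss 27%.
- n = 2 × (20.7 × (1.960 + 1.282) / 6.0)² = 250.1, so 251 per arm
- (1 − 0.6²) × 251 = 160.6, so 161
- 161 / 0.73 = 220.5, so 221; 3 × 221 = 663

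The stated 663 reproduces and is not in question.

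**5. Illustrative size for OHIP-TMD.** Standard error of a pairwise difference: 20.7 × √(1 − 0.36) × √(2/161) = 16.56 × 0.1115 = 1.85. Let pT and pA be the shares of TAU and of an injection arm whose week-36 set is taken before a switch. Let g be the points by which the true week-36 score is better than the pre-switch score. Then

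shift in (injection − TAU) = −(pT − pA) × g

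and the chance of a false superiority finding on OHIP-TMD alone, when the true difference is 0, is Φ(−shift/1.85 − 1.96). The documents give none of pT, pA or g; all three are assumed.

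| pT | pA | g | Shift | False-positive rate (nominal 2.5%) |
|---|---|---|---|---|
| 5% | 5% | 3–12 | 0 | 2.5% |
| 10% | 5% | 6 | −0.3 | 3.6% |
| 15% | 5% | 6 | −0.6 | 5.1% |
| 20% | 10% | 12 | −1.2 | 9.5% |
| 20% | 5% | 12 | −1.8 | 16.2% |

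A negative shift favours the injection. It reverses if more injection than TAU participants are affected, or if scores worsen after the switch. Superiority also requires significance on CPI, so these rates describe one co-primary and not the trial decision. The same formula applies to CPI; no separate CPI illustration was run.

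**The case against.** The best defence is that no sentence says an early set replaces week 36. Section 7.6 returns participants to the regular schedule, which contains a week-36 visit, and 7.5 asks for week 36 at the least. A site could read these together and collect both sets. The request is also voluntary, and which dated questionnaire counts as week 36 is the kind of windowing rule that a SAP may settle. Part of this stands: the text is ambiguous and some sites may do the right thing. But 7.5 and the schedule note point to the set after the one just completed, and after week 36 there is none. A SAP can reclassify an early value, but it cannot supply a value that was never collected.

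A reader might infer that 7.5 and 7.6 bring forward or end week 36 after any treatment change. The documents do not support that: the first three rows of the first table leave week 36 in place, and 7.5 protects it for discontinuers.

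A reader might also infer that the withdrawal grounds in 7.5 contradict the estimand. They do not. Withdrawal is discretionary and produces missing data, not a mistimed value. The model uses all timepoints under missing at random, the sample size allows for 27% loss, and attrition is monitored. What remains is narrower: withdrawal for deterioration or intolerance is plausibly related to outcome, and 7.5 does not provide for asking such participants to continue questionnaires.

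**Conclusion.** The point holds in a narrow form. For participants who discontinue trial treatment and start a new TMD therapy between the week-24 and week-36 sets, the switching rule as worded yields pre-switch co-primary values with no later set. That conflicts with the treatment-policy strategy for alternative treatments, the ±7-day window and the recall periods. The group is probably concentrated in TAU, so the effect may differ by arm.

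Its size is unknown. Over the assumed range the shift runs from 0 to about 1.8 OHIP-TMD points, at most 1.8/6.0 = 30% of the minimally important difference. The upper end needs 20% against 5% affected and a 12-point missed change within one 12-week interval; more modest assumptions give 0.3 to 0.6 points. A reader might conclude that the primary result must be seriously biased in favour of injections. The documents support neither that size nor that direction. The change should be made because the lost values cannot be recovered and the repair is cheap. The sample size of 663 is unaffected.

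**What to change.** - In 7.5, 7.6 and the schedule note: define the set taken before a new therapy as an additional, dated assessment that never replaces a scheduled one. Still collect CPI and OHIP-TMD at week 36 ±7 days, and let only that set supply the 36-week outcome.
- In 7.5: add that a participant whom the investigator withdraws for deterioration, toxicity, tolerance problems or non-compliance is asked, with consent, to continue at-distance questionnaires including week 36. Leave the list of withdrawal grounds as it is.
- Reconcile 7.5, 7.6 and the schedule note with 10.2.1.

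The cost is protocol and CRF wording and one extra questionnaire set for each participant who switches, with some added burden for them. It needs no additional participants or visits. It changes what is collected and when, not when treatment stops or a new therapy begins.
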